8.5.4. Efficacy Analyses

To evaluate the incidence of COVID-19 after vaccination with mRNA-1273 or placebo, the incidence rate will be provided by vaccination group, calculated as the number of cases divided by the total person-time. The incidence rate ratio of mRNA-1273 versus placebo may be provided with its 95% CI computed using the exact method conditional upon the total number of cases adjusted by the total person-time.

For SARS-CoV-2 infection (serologically confirmed SARS-CoV-2 infection or COVID-19), regardless of symptomatology or severity, infection rate will be provided by vaccination group. The infection rate ratio of mRNA-1273 versus placebo may be provided with its 95% CI using the exact method conditional upon the total number of cases adjusted by the total person-time. The incidence rate of asymptomatic SARS-CoV-2 infection will also be provided.

The secondary efficacy analyses will be performed in the PP set, with sensitivity analyses in the FAS, mITT Set, and mITT1 Set.

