Unsolicited treatment-emergent AEs (TEAEs) up to 28 days after any dose were more common in the mRNA-1273 group than in the placebo group. Imbalances in unsolicited TEAEs up to 28 days after any dose was primarily attributable to events related to reactogenicity. The incidence of MAAEs within 28 days of injection was generally similar between the mRNA-1273 and placebo groups. The incidence of unsolicited severe TEAEs and serious TEAEs in the 28 days after any dose was low overall and generally similar in participants who received mRNA-1273 and those who received placebo. Unsolicited TEAEs, including MAAEs, up to

28 days after any dose assessed by the investigator as related to study treatment were more frequently reported in the mRNA-1273 group than in the placebo group.

Data from interim data cut of 31 Jan 2022 showed consistent immunogenicity and safety results as the first interim results (08 May 2021). The evidence from the 08 May 2021 data cutoff infers effectiveness, suggesting that mRNA-1273 is effective in preventing COVID-19, and the known and potential benefits of mRNA-1273 when used to prevent COVID-19 outweigh the known and potential risks.

The updated data collected as of 31 Jan 2022 included: (i) VE of the blinded phase updated as of 31 May 2021; (ii) COVID-19 cases as of 31 Jan 2022; and (iii) safety data from all mRNA-1273 recipients for the blinded and open-label phases of the study.

Vaccine efficacy through 31 May 2021 was 100% (95% CI: 61.2%, not estimated [NE]) using the P301 case definition and 89.9% (95% CI: 51.0%, 98.9%) using the CDC case definition. The updated analysis confirms results provided in the EUA Amendment submitted on 09 Jun 2021 based on the 08 May 2021 data cutoff). Beyond 31 May 2021, the loss of placebo participants precluded meaningful analysis of VE. Long-term assessment of monthly incidence rates among all participants who received mRNA-1273 as randomized and remained on study up to 31 Jan 2022 (combined blinded and unblinded) shows low monthly incidence rates of COVID-19 until November 2021. Not unexpectedly, an increase in COVID-19 incidence rates was observed in December 2021 and January 2022, when the Omicron variant prevailed.

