
 To evaluate the persistence of the immune response of mRNA-1273 vaccine (100 µg) administered in 2 doses 28 days apart, as assessed by the level of SARS-CoV-2 S2P-specific bAb through 1 year after Dose 2 To evaluate the persistence of the immune response of mRNA-1273 vaccine (100 µg) administered in 2 doses 	
 The GM value of SARS-CoV-2 S2P-specific bAb on Day 1, Day 57 (1 month after Dose 2), Day 209 (6 months after Dose 2), and Day 394 (1 year after Dose 2) The GM values of SARS-CoV-2-specific nAb on Day 1, Day 57 (1 month after Dose 2), Day 209

Objectives	Endpoints
28 days apart, as assessed by the level of nAb through 1 year after Dose 2	(6 months after Dose 2), and Day 394 (1 year after Dose 2)

 To evaluate the effect of mRNA-1273 on the incidence of SARS-CoV-2 infection compared with the incidence among placebo recipients 	
 The incidence of SARS-CoV-2 infection (symptomatic or asymptomatic infection) counted starting 14 days after the second dose of IP SARS-CoV-2 infection will be defined in participants with negative SARS-CoV-2 at baseline: 
 bAb level against SARS-CoV-2 nucleocapsid protein negative at Day 1 that becomes positive (as measured by Roche Elecsys) at Day 57 or later, OR Positive RT-PCR counted starting 14 days after the second dose of IP

 To evaluate the incidence of asymptomatic SARS-CoV-2 infection after vaccination with mRNA-1273 or placebo 	
 The incidence of asymptomatic SARS-CoV-2 infection measured by RT-PCR and/or bAb levels against SARS-CoV-2 nucleocapsid protein (by Roche Elecsys) counted starting 14 days after the second dose of IP in participants with negative SARS-CoV-2 at baseline

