
 To evaluate the incidence of COVID-19 after vaccination with mRNA-1273 or placebo. COVID-19 is defined as clinical symptoms consistent with SARS-CoV-2 infection AND positive RT-PCR for SARS-CoV-2 	
 The incidence of the first occurrence of COVID-19 starting 14 days after the second dose of IP, where COVID-19 is defined as symptomatic disease based on the following criteria: 
 The participant must have experienced at least TWO of the following systemic symptoms: Fever ($\geq 38^{\circ}\text{C}/\geq 100.4^{\circ}\text{F}$), chills, myalgia, headache, sore throat, new olfactory and taste disorder(s), OR The participant must have experienced at least ONE of the following respiratory signs/symptoms: cough, shortness of breath or difficulty breathing, OR clinical or radiographical evidence of pneumonia; AND The participant must have at least 1 NP swab, nasal swab, or saliva sample (or respiratory sample, if hospitalized) positive for SARS-CoV-2 by RT-PCR
Exploratory Objectives	Exploratory Endpoints

 To evaluate the genetic and/or phenotypic relationships of isolated SARS-CoV-2 strains to the vaccine sequence 	
 Alignment of genetic sequence of viral isolates with that of the vaccine sequence and comparison of bAb and nAb titers against isolated strain relative to prototype vaccine strain

Objectives	Endpoints

 To describe the ratio or profile of specific bAb relative to nAb in serum To characterize the clinical profile and immune responses of participants with COVID-19 or with SARS-CoV-2 infection 	
 Relative amounts or profiles of S protein-specific bAb and specific nAb levels/titers in serum Description of clinical severity and immune responses of participants who are identified as infected by SARS-CoV-2 (COVID-19)

 To evaluate the incidence of asymptomatic SARS-CoV-2 infection after vaccination with mRNA-1273 or placebo in participants with serologic evidence of infection at baseline 	
 GM value and GMFR of bAb levels against SARS-CoV-2 nucleocapsid protein (quantitative IgG) and % of participants with 2x, 3x, and 4x rise of bAb relative to baseline
Exploratory Objectives for Part 1B:	Exploratory Endpoints for Part 1B:

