The secondary case definition of COVID-19 is defined as the following systemic symptoms: fever (temperature $>38^{\circ}\text{C}/\geq 100.4^{\circ}\text{F}$), or chills, cough, shortness of breath or difficulty breathing, fatigue, muscle aches, or body aches, headache, new loss of taste or smell, sore throat, congestion or runny nose, nausea, or vomiting or diarrhea AND a positive NP or nasal swab or saliva sample for SARS-CoV-2 by RT-PCR.

Death attributed to COVID-19 is defined as any participant who dies during the study with a cause directly attributed to a complication of COVID-19.

SARS-CoV-2 Infection:

- SARS-CoV-2 infection is defined in participants with SARS-CoV-2 negative at baseline:
 - bAb level against SARS-CoV-2 nucleocapsid protein negative at Day 1, which becomes positive post baseline, OR
 - Post baseline-Positive RT-PCR.

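### The Section 8.5.4 bracket narrows the RT-PCR limb of the SARS-CoV-2 infection endpoint to symptomatic cases, so PCR-positive non-seroconverters outside the COVID-19 definition are not counted

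*Protocol*

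**What the plan says.** **Endpoint.** Table 1 in Section 2, repeated in the synopsis, defines infection among participants negative at baseline by two alternatives. The serological limb is "bAb level against SARS-CoV-2 nucleocapsid protein negative at Day 1 that becomes positive (as measured by Roche Elecsys) at Day 57 or later, OR" and the virological limb is "Positive RT-PCR counted starting 14 days after the second dose of IP". Neither asks for symptoms. Section 7.4.1 also has two limbs, the second being "Post baseline-Positive RT-PCR". It words the counting window differently from Table 1 but again attaches no symptom condition.

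**Analysis.** Section 8.5.4 and the Efficacy Analyses part of the synopsis say: "For SARS-CoV-2 infection (serologically confirmed SARS-CoV-2 infection or COVID-19), regardless of symptomatology or severity, infection rate will be provided by vaccination group". A rate ratio with an exact conditional interval may follow, and the same paragraph promises an asymptomatic infection rate.

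**COVID-19.** Table 1 says "COVID-19 is defined as clinical symptoms consistent with SARS-CoV-2 infection AND positive RT-PCR for SARS-CoV-2", and its criteria require two systemic symptoms or one respiratory sign in addition to the positive RT-PCR. Section 7.4.1 adds a broader alternative: "The secondary case definition of COVID-19 is defined as the following systemic symptoms", followed by a longer symptom list and a positive RT-PCR. Section 8.5.4 does not say which of the two it means.

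**Asymptomatic infection.** Table 1 describes this endpoint as "The incidence of asymptomatic SARS-CoV-2 infection measured by RT-PCR and/or bAb levels against SARS-CoV-2 nucleocapsid protein".

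**The concern.** The comparison of infection between mRNA-1273 and placebo is a stated secondary objective. The endpoint table and the analysis section give different rules for who counts as infected. The analysis rule is the narrower one, because its only RT-PCR route runs through a symptomatic case definition. Two programmers working from the two sections would derive different flags. The analysis as written would also undercount the trial's own endpoint, and its asymptomatic count would not be contained in its total. With few events, reclassifying one or two vaccine-arm cases could move a rate ratio visibly.

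**Working it through.** **1. The two rules as sets.** Let S = nucleocapsid seroconversion, P = positive RT-PCR in the counting window, and C = meets the COVID-19 symptom criteria.

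- Table 1: S or P
- Section 8.5.4: S or (P and C)
- Difference: P and not C and not S

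The participants lost are exactly those who are PCR positive, do not meet the COVID-19 definition and never seroconvert. PCR positives who seroconvert are kept through S. PCR positives with qualifying symptoms are kept through C.

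**2. Can the lost group occur?** Yes. Part 1A takes swabs whatever the symptoms at Day 57 (Section 3.1.1.1) and Day 209 (Table 10), and exposure alone triggers a swab (Section 7.1.6). Symptoms that trigger an illness visit but fall short of the Table 1 criteria (for example, one systemic symptom only) are a further source.

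**3. Internal consistency.** An asymptomatic PCR-only case satisfies the asymptomatic endpoint (RT-PCR and/or antibody) but not the Section 8.5.4 bracket. It is in the part and not in the whole.

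**4. Size in general.** The protocol gives no figures for this. With assumed values only: if 20% to 50% of endpoint infections are PCR positive outside COVID-19, and 50% to 90% of those seroconvert, the share missed runs from 0.20 x 0.10 = 2% to 0.50 x 0.50 = 25%.

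**5. A worst case from the printed interim results.** Section 1.2.2.5 reports vaccine efficacy through 31 May 2021 of 100% (lower limit 61.2%) by the P301 case definition and "89.9% (95% CI: 51.0%, 98.9%) using the CDC case definition". It prints no case counts, but they can be back-solved from the exact conditional interval. With v vaccine cases, p placebo cases and person-time ratio k (vaccine to placebo):

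- VE = 1 - (v/p)/k
- each limit = 1 - [q/(1 - q)]/k, where q is a Clopper-Pearson limit for v out of v + p

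The CDC result fits only 2 vs 9, at k of about 2.19:

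- VE = 1 - (2/9)/2.19 = 1 - 0.1015 = 89.9%
- Clopper-Pearson limits for 2/11 are 0.0228 and 0.5178
- lower VE limit = 1 - (0.5178/0.4822)/2.19 = 51.0%
- upper VE limit = 1 - (0.0228/0.9772)/2.19 = 98.9%

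The P301 result at the same k fits 0 vs 6:

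- upper limit for 0/6 is 1 - 0.025^(1/6) = 0.4593
- lower VE limit = 1 - (0.4593/0.5407)/2.19 = 61.2%

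Taken alone, the P301 result would also fit other pairs at other ratios (0 vs 5 near 2.81, 0 vs 7 near 1.79). It is the shared ratio that fixes 0 vs 6.

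The difference is (2 + 9) - (0 + 6) = 5 of 11 cases: 2 of 2 on vaccine and 3 of 9 on placebo. If none of the five seroconverted, the symptomatic component gives a rate ratio of 0 (0 vs 6; 95% CI 0 to 0.39) under Section 8.5.4, against 0.10 (2 vs 9; 0.01 to 0.49) under Table 1. If all five seroconverted, the two rules agree on these cases.

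**The case against.** The strongest reply is that the bracket is a loose gloss and not a competing case rule. Two formal definitions keep a stand-alone RT-PCR limb, the sentence itself disclaims symptomatology and severity, and asymptomatic PCR-only cases are still reported in their own rate. This shows the likely intent, but it does not repair the rule: the bracket states what is counted, and taken literally its only PCR route requires symptoms.

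Second, a reader might infer that the RT-PCR limb has been dropped and that all PCR-confirmed infections outside the COVID-19 definition go uncounted. The protocol does not support that. COVID-19 itself requires RT-PCR, and Part 1A blood is drawn at Day 57, Day 209 and Day 394, so seroconverting PCR positives are still captured.

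Third, a reader might infer from the interim figures that the narrower rule favours the vaccine. That is not shown. No section reports nucleocapsid serology for any of these cases. Section 1.2.2.5 does not tie its two case definitions to those in Section 7.4.1, and it gives no counting start for the 31 May 2021 figures. If COVID-19 in Section 8.5.4 includes the broader secondary definition, and that is the CDC definition, all 11 symptomatic cases are counted and only asymptomatic PCR positives without seroconversion are lost. Even in the worst case the two intervals overlap almost entirely, and neither is the infection rate ratio, which also includes seroconversions and asymptomatic infections whose numbers are not given.

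Fourth, the consequence is limited. The infection rate ratio is only something that may be provided, it carries no hypothesis or power statement, and it lies outside the testing sequence in Section 8.6. This stands.

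**Conclusion.** The analysis text is wrong as written for a secondary endpoint. The mismatch between Table 1 with Section 7.4.1 on one side and Section 8.5.4 with the synopsis on the other is plain from the text. It is not a detail that a protocol leaves to the SAP, because the protocol states both rules and they differ.

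The effect on the rate ratio is unknown in both size and direction. The figure of up to 5 of 11 symptomatic PCR-confirmed cases depending on seroconversion is a worst case. It assumes that:

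- both interim results share one person-time ratio;
- they use the Table 1 counting window;
- the P301 definition corresponds to the Table 1 definition, and its cases are a subset of the CDC-definition cases;
- COVID-19 in Section 8.5.4 means the narrower Table 1 definition.

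Among those five, anything from none to all may be lost, depending on seroconversion. Asymptomatic PCR positives without seroconversion would add to the loss in a number that the protocol does not give. The primary immunogenicity objective and the stated power are unaffected.

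**What to change.** In Section 8.5.4 and in the Efficacy Analyses part of the synopsis, replace the bracket with the Table 1 definition: in participants SARS-CoV-2 negative at baseline, nucleocapsid antibody negative at Day 1 and positive at Day 57 or later, OR any positive RT-PCR (scheduled, illness or exposure swab) from 14 days after the second dose, regardless of symptoms. The asymptomatic count then becomes a true subset of the infection count. The cost is a text edit in two places and re-derivation of one flag from data already collected.

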8.5.5. Long-term Analysis (Including Part 1B)

Long-term analysis will be performed including data collected in the Open-label Observational Phase (Part 1B), and prior to BD if a BD is received. The analysis will include participants who are randomized to mRNA-1273 in Part 1A and remained in the study with or without unblinding, and participants who are originally randomized to placebo and later crossed over to receive mRNA-1273 in Part 1B after unblinding. Long-term analysis of applicable safety, efficacy, and immunogenicity endpoints will be summarized descriptively by treatment cohort as defined in [Table 9](#) without treatment group comparison.

In the long-term safety analysis, unsolicited AEs (SAE, AESI, MAAE, and AE leading to discontinuation) and deaths will be summarized.

In the long-term immunogenicity analysis, nAb and bAb values will be summarized at specified timepoints.

In the long-term efficacy analysis, the incidence rates of COVID-19 and of SARS-CoV-2 infection cases will be counted starting 14 days after the second dose of IP for participants in treatment cohort of mRNA-1273 or starting 14 days after the second dose of mRNA-1273 for participants in the Placebo-mRNA-1273 cohort. Incidence rate with 95% CI adjusting for

person-time will be provided. The incidence rate of asymptomatic SARS-CoV-2 infection will also be provided.

Table 9: Treatment Cohorts for the Long-term Analysis

Long-term Treatment Cohort	Description
mRNA-1273	Participants randomized to mRNA-1273 in the Blinded Phase
Placebo-mRNA-1273	Participants randomized to Placebo in the Blinded Phase who crossed over to mRNA-1273 in the Open-label Observational Phase

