3.2. Scientific Rationale for Study Design

The single age cohort in this Phase 2/3 study, 12 to < 18 years of age, was established to understand the tolerability and immunogenicity of 100 µg (Part 1A) and 50 µg (Part 1C-1, Part 1C-2, and Part 2) mRNA-1273, as well as 50 µg (Part 3) mRNA-1273.222 in an adolescent population. The lower age boundary used in this study is consistent with the definition of adolescence provided by the American Academy of Pediatrics (Hardin et al 2017).

With SARS-CoV-2 expected to be circulating in the general population during the study, all participants will provide preinjection blood samples and postinjection blood samples for Ab analysis through 12 months after the last dose of IP during Part 1A, Part 2, and through 6 months (for participants who receive Dose 2) or 1 to 6 months after the last dose of IP in Part 3 of the study. In addition, participants will have NP or nasal swab samples collected before the injection on Day 1 (Part 1A, Part 1C, Part 2, and Part 3), Day 29 (Part 1A, Part 2, and Part 3), Day 149 (Part 2 participants who receive the booster dose), and Day 181 (Part 3 participants who receive Dose 2); additional timepoints are in the SoA (Table 10 and Table 12 through Table 18). Furthermore, with any signs or symptoms or MAAE suggesting SARS-CoV-2 infection in a participant, an additional nasal or NP swab sample and a blood sample will be taken to confirm the diagnosis of SARS-CoV-2 via serology and RT-PCR. Additionally, clinical information will be carefully collected to evaluate the severity of the clinical case.

As it is possible that participants are naturally exposed to SARS-CoV-2 through community exposure, the NP or nasal swab samples collected before study injection and the serologic assays for Ab responses to nonvaccine antigen(s) may help discriminate between natural infection and vaccine-induced Ab responses, should such discrimination be needed.

Part 1B, is the Open-label Observational Phase. During Part 1B of the study, all ongoing study participants were permitted (a) to be informed of the availability and eligibility criteria of any COVID-19 vaccine made available under an EUA and (b) to schedule a study visit to know their original group assignment (placebo vs. mRNA-1273 vaccine). Part 1B also provided the opportunity for eligible study participants who previously received placebo to receive 2 doses of mRNA-1273 vaccine under open-label conditions.

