8.4. Analysis Sets

The analysis sets are defined in [Table 7](#).

Table 7: Analysis Sets

Analysis Set	Description
Randomization Set	All participants who are randomized, regardless of the participants' treatment status in the study.
FAS	All randomized participants who received at least 1 injection of IP.
Immunogenicity Subset	A subset of participants in the FAS will be selected for immunogenicity testing.
PP Immunogenicity Subset	A subset of participants in the FAS will be selected for immunogenicity testing. The PP Immunogenicity Subset includes participants selected for the Immunogenicity Subset who received planned doses of study vaccination per schedule, complied with immunogenicity testing schedule, and have no major protocol deviations that impact key or critical data. Participants who are seropositive at baseline will be excluded from the PP Immunogenicity Subset. The PP Immunogenicity Subset will be used for analyses of immunogenicity unless specified otherwise.
PP Set for Efficacy	All participants in the FAS who received planned doses of study vaccination, had no immunologic or virologic evidence of prior COVID-19, and have no major protocol deviations that impact key or critical efficacy data.
Solicited Safety Set	The Solicited Safety Set consists of FAS participants who contributed any solicited AR data. The Solicited Safety Set will be used for the analyses of solicited ARs.
Safety Set	All randomized participants who receive at least 1 dose of IP. The Safety Set will be used for all analyses of safety except for the solicited ARs.
mITT Set	All participants in the FAS who have no serologic or virologic evidence of prior SARS-CoV-2 infection before the first dose of IP (both negative RT-PCR test for SARS-CoV-2 and negative serology test based on bAb specific to SARS-CoV-2 nucleocapsid) at baseline.
mITT1 Set	All participants in the mITT Set excluding those who received the wrong treatment (ie, at least 1 dose received is not as randomized or planned).
PP Immunogenicity Subset for BD phase	The PP Immunogenicity Subset for BD phase includes participants who received planned BD per schedule, complied with immunogenicity testing schedule, and have no major protocol deviations that impact key or critical data, with prebooster negative or positive SARS-CoV-2. The PP Immunogenicity Subset with prebooster negative SARS-CoV-2 will be used for the primary immunogenicity analysis.

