based on the t-distribution of the log transformed values then back transformed to the original scale. Descriptive summary statistics including median, minimum, and maximum will also be provided. The immunogenicity descriptive summaries will be provided in the participants who have available nAb and bAb assay results for the specified timepoints.

In the Booster Phase, the incidence rate of the first occurrence of symptomatic COVID-19 starting 14 days after the BD will be summarized by prebooster SARS-CoV-2 status. The incidence rate of SARS-CoV-2 infection (symptomatic or asymptomatic infection) starting 14 days after the BD, and the incidence rate of asymptomatic SARS-CoV-2 infection starting 14 days after the BD will be summarized. The incidence rates with 95% CI will be computed adjusting for person-years starting from BD-Day 1 in Part 1C-1.

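### The stated populations for the antibody-persistence geometric means keep samples taken after a breakthrough infection, so persistence of the vaccine response can be overstated

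*Protocol*

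**What the plan says.** **Objective and endpoint.** Table 1 in Protocol Section 2 sets a Part 1A secondary objective that begins "To evaluate the persistence of the immune response of mRNA-1273 vaccine" and continues "as assessed by the level of SARS-CoV-2 S2P-specific bAb through 1 year after Dose 2". A parallel objective covers neutralizing antibody. The endpoint is "The GM value of SARS-CoV-2 S2P-specific bAb on Day 1, Day 57 (1 month after Dose 2"), with Day 209 and Day 394 following. It carries no condition on infection. Persistence is exploratory in Part 1C (to BD-Day 361), Part 2 (to Day 394) and Part 3 (to Day 181).

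**Who is analysed.** Table 7 in Section 8.4 makes the PP Immunogenicity Subset the default for immunogenicity. Its only infection rule is "Participants who are seropositive at baseline will be excluded from the PP Immunogenicity Subset". The booster-phase set includes participants who were SARS-CoV-2 negative or positive before the booster; the restriction to negatives applies to the primary booster analysis alone. The Part 3 set likewise keeps both baseline statuses.

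**What is summarized.** Section 8.5.3 gives geometric means at every timepoint. Section 8.5.5 adds: "In the long-term immunogenicity analysis, nAb and bAb values will be summarized at specified" timepoints, using data collected before the booster where one is given. For Part 1C-1, Section 8.5.6.1 states: "The immunogenicity descriptive summaries will be provided in the participants who have available nAb and bAb assay results", out to BD-Day 361, and by prebooster status if applicable. Sections 8.5.6.2, 8.5.7 and 8.5.8 give similar summaries by timepoint for Parts 1C-2, 2 and 3, with no rule on later infection.

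**What the protocol knows about infection.** Section 3.2 says that predose swabs and nonvaccine-antigen serology "may help discriminate between natural infection and vaccine-induced Ab responses, should such discrimination be needed". Section 1.2.2.5 reports that "an increase in COVID-19 incidence rates was observed in December 2021 and January 2022", when Omicron prevailed.

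**The concern.** A persistence endpoint asks how long the antibody made by the vaccine lasts. Spike-binding and neutralizing antibody cannot answer that unaided once participants have been infected, because infection raises the same analytes. The protocol itself reports higher titres in previously infected participants (Sections 1.2.2.3 and 3.2).

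Section 8.5.5 does recognise one event that breaks the interpretation, the booster dose, and cuts the data there. It sets no matching rule for infection, although the next paragraph counts infections in the same cohorts for incidence.

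The direction of the error is unhelpful. The more breakthrough infection a cohort has, the higher its late geometric mean, so weaker protection would look like better persistence.

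**Working it through.** The protocol gives no figure for this effect, so there is none to reproduce. The check has three steps.

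**1. Does any stated rule remove post-infection samples?**
- Part 1A: the default set excludes on baseline serostatus only. Section 8.5.3 gives geometric means at each timepoint. The only cut in Section 8.5.5 is the booster.
- Part 1C-1: everyone with assay results, split by prebooster status if applicable. That split does not address infection after the booster.
- Part 1C-2 and Part 2: the PP Immunogenicity Subset with available results.
- Part 3: both baseline statuses kept, summarized by timepoint.

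No rule in any part acts on infection between baseline (or booster) and the sample.

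**2. Do the late samples fall in a period of infection?**
- Part 1A: estimated first enrollment is 30 Nov 2020 (Synopsis). Day 394 is Day 1 + 393 days = 28 Dec 2021. The ±14-day window in Table 10 runs from 14 Dec 2021 to 11 Jan 2022. This is inside the December 2021–January 2022 rise, and later enrollees reach Day 394 after this date.
- Part 1C-1: the booster entered with Amendment 3, dated 04 Nov 2021 (Appendix 5). BD-Day 181 is therefore nominally no earlier than 04 Nov 2021 + 180 days = 3 May 2022, and BD-Day 361 no earlier than + 360 days = 30 Oct 2022.
- Part 2 was added by Amendment 4 (25 Jan 2022) and Part 3 by Amendment 5 (11 Oct 2022), both after Omicron was detected in November 2021 (Section 1.1).

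One limit applies to Day 394. The long-term analysis uses data before the booster, and the placebo-crossover schedule (Table 12) ends at OL-D178. In that analysis Day 394 values therefore come only from unboosted mRNA-1273 recipients.

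**3. How large could the effect be?** Let m be the mean log titre of the uninfected, f the share of samples taken after infection, and R the infected-to-uninfected geometric mean ratio. The overall log mean is

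(1 − f)·m + f·(m + ln R) = m + f·ln R,

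so the geometric mean is multiplied by R^f. Neither f nor R is in the protocol. For assumed values:

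| R | f = 10% | f = 30% | f = 50% |
|---|---|---|---|
| 2 | ×1.07 | ×1.23 | ×1.41 |
| 10 | ×1.26 | ×2.00 | ×3.16 |

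For example, 2^0.1 = 1.07 and 10^0.5 = 3.16.

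**The case against.** The strongest reply is that Section 8.5.3 leaves the complete set of immunogenicity analyses to the SAP, which is not at hand and could censor or stratify by infection. That limits what can be claimed. A reader might infer that the trial does report infection-boosted antibody as vaccine persistence, and the protocol alone does not show that. But the protocol is not merely silent. It names who is analysed, and following that text keeps the post-infection samples in.

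A second reply is that infection is reported elsewhere. Section 2 has an exploratory objective describing immune responses in infected participants, and incidence is tabulated in the same long-term and booster analyses. Both help a reader, but neither takes infection-raised antibody out of the persistence geometric means.

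Third, an all-sample summary is a legitimate description, and excluding samples after infection conditions on a post-vaccination outcome. If those infected tended to have lower titres, the remainder would be selected high responders. This stands, and it is why neither summary should be used alone.

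Three stronger readings are tempting but unsupported:
- *Positive participants are dropped from all persistence summaries.* The booster and Part 3 sets keep them.
- *The ratio of 4.322 in Section 1.2.2.5 measures the inflation.* It compares adolescents infected before vaccination, after one 50 µg dose, with uninfected young adults in Study P301 after two 100 µg doses. It is not a multiplier for infection after vaccination.
- *The bias can be judged against the 1.5-fold noninferiority margin, or calls for extra sensitivity analyses at the tested visits.* That margin applies to comparisons at Day 57, BD-Day 29 and Part 3 Day 29, which do not use the late samples. No problem has been shown at those visits.

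**Conclusion.** The point holds for the protocol as written. Its populations for the persistence geometric means take account of infection only at baseline or, for the booster, by prebooster status if applicable. The late visits fall in or after the Omicron rise, so these geometric means can overstate persistence of the vaccine response.

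The direction rests on R being above 1. The size is unknown, and the range of ×1.07 to ×3.16 reflects assumed inputs, not estimates. The Part 1A dates rest on the estimated first-enrollment date.

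The affected endpoints are secondary in Part 1A, exploratory in Parts 1C, 2 and 3, and descriptive throughout. No hypothesis test or success criterion changes. This is worth correcting because conclusions about durability would rest on these numbers.

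**What to change.** In Sections 8.5.3, 8.5.5 and 8.5.6 to 8.5.8, or in the SAP by reference, state that each persistence geometric mean is reported in two ways:
- with all samples;
- with a participant's samples excluded from the first post-baseline (or post-booster) evidence of infection onward. Evidence means anti-nucleocapsid seroconversion or a positive RT-PCR, or RT-PCR only for participants already anti-nucleocapsid positive.

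Give the number infected by each visit beside both, and draw persistence conclusions from the two together.

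The cost is some wording and one further set of tables. Section 7.2 already provides for anti-nucleocapsid testing of all participants at specified timepoints, and RT-PCR results come from scheduled swabs and illness visits. The infection-free summary will have fewer samples, wider intervals and possible selection. Detection will be weaker where only RT-PCR is usable: Table 13, for instance, schedules a swab only at BD-Day 1, so later infections in prebooster-positive participants would be found only through illness visits.
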